#### Obtaining Consent

Participants provide written consent to the study. the ANP liaises with the Mental Health team to identify eligible patients and ensure the team are happy for the service user to be approached about the study.

Service Users receive an introduction letter and a copy of the patient information sheet informing them of the study and advising that they may be asked to participate in the study at their next outpatient appointment or home visit. The patient meets the data collector who explains the study, answer any questions and obtains written consent.

Participants are given the right to withdraw from participation should they wish to, as well as to opt out of answering questions. Participants have a right to withdraw without explanation. Patients provide permission to collect identifying information to allow follow-up. As soon as follow-up is complete, all identifying information is removed from the dataset so the data becomes de-identified and the participant is allocated a study ID.

#### Data Collection

Following consent the patient participates in face-to-face interviews with the ANP where a structured questionnaire will be completed (there are no qualitative interviews). The questionnaire has been developed by an expert group of geriatricians, and old age psychiatry.

Data collection includes socio-demographic details, MH diagnosis, co-morbidities,

#### Outcomes:

Sarcopenia: The SARC-F (tool title not an abbreviation) is a screening tool for sarcopenia ((Malmstrom et al 2013). SARC-F comprises five components using self-report on: strength, assistance walking, rise from a chair, climb stairs, and falls. SARC-F scale scores range from 0 to 10 (i.e. 0–2 points for each component; 0 = *best* to 10 = *worst*) and are dichotomized to represent symptomatic (4+) vs. healthy (0–3) status (Malmstrom et al 2016).

Frailty: Clinical Frailty Scale (CSF) is a judgement-based frailty tool that evaluates specific domains including comorbidity, function, and cognition to generate a frailty score ranging from 1 (very fit) to 9 (terminally ill), a higher score indicates poorer physical and cognitive function (Rockwood et al 2005, Church 2020).

The Global Physical Health Scale v1.2 is a four-item validated general health questionnaire (Riley et al 2010, Hays et al 2015). Four items are used to assess global physical health. Three items (rate your physical health, everyday activities, rate your fatigue) of these are administered using five-category response scales. Higher scores indicated better health. One item (rating of pain on average) uses a response scale of 0–10 that is recoded to five categories (0 = 1; 1-3 = 2; 4-6 = 3; 7-9 = 4; 10 = 5), the scale is then reverse coded, i.e. 0 (no pain) = 5). Overall scores range from 5 to 20 indicating best possible physical health (PROMIS 2021)

Mental health: Bespoke mental health items. Two items (rate your overall mental health, rate your mood (sense of well-being) over past seven days) were rated on a 5 point scale (excellent = 5; very poor = 1). Items are presented separately, scores range from 1 to 5, higher score indicates better mental health.

Exercise: Two items from Yale Physical Assessment Scale (vigorous exercise frequency and duration over past 7 days, and Walking for exercise frequency and duration over past 7 days) ((De Abajo et al., 2001). Frequency was rated on a 4 point scale (not at all=0; 1-2 times=1, 3-4 times=2 or >4 times=3) Duration (0=not applicable, 1=10-30 mins, 2=31-60 mins, 3> 60 mins. Scores are calculated by multiplying Frequency score X Duration score (no weight was applied). Higher scores indicate more activity. Items were not combined for an overall exercise score.

Post intervention, we added an additional question specific to the exercises on the information leaflet

In the past week (7 days) have you completed the exercises on the information leaflet

Frequency (None=0, 1 day=1, 2 days=2; 3 days=3, 4 days=4, 5 days=5); X Duration (none =0; 10 mins=1, 11-20 mins=2, 21-30 mins=3, >30 mins=4). Higher values indicate greater exercise intensity (min score 0 to 20).

Nutrition: Simplified nutritional appetite questionnaire (SNAQ) is a four item scale (rate appetite, When I eat I feel full, food tastes, normally I eat) are rated on a five point scale (1 to 5). Total possible score range from 5 to 20, higher scores indicate better appetite. SNAQ score 14 indicates significant risk of at least 5% weight loss within six months (Kruizenga et al., 2005).

Protein intake: Patients self-reported the number of protein portions eaten in the previous day: Protein was categorised as: meat/fish; milk/dairy; eggs/cheese; vegetable protein

The one-month questionnaire focused on acceptability of intervention and ease of use.

Patients are also be asked to give qualitative feedback on the intervention.

The 3-month questionnaire repeated the baseline measures and adherence questions.

Implementation outcomes:

Acceptability (Bespoke item)

One item measures acceptability: The exercise and nutrition advice was acceptable to me (made sense) rated on a 5 point Likert scale (1=strongly disagree to 5 strongly agree)

Ease of Use (Bespoke item)

One item measured Ease of Use ' To what extent was it easy to incorporate the exercise and nutrition advice into your daily routine rated on a five point Likert scale (1=very difficult to 5 very easy)

Recommend to others (bespoke item)

The final item sought participants opinion on 'recommending the intervention to others. 'In your opinion, should we continue to offer this advice and information leaflets to other people attending our service? With three response options Yes/No/ Don't know

A study log is maintained recording the number of eligible patients invited to participate, the number of patients who refused, reasons for refusal, number of patients who consented, number of patients who completed 1-month and 3-month follow-up.

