There is a strong evidence base for reversal of frailty in the general population (Reference systematic reviews), interventions focus on exercise with or without protein based nutrition. However, there is very few studies that have translated this research to older peoples living with severe mental illness.

A recent RCT undertaken in Irish GP practices identified the acceptability and effectiveness of a low intensity intervention combining brief (<10 mins) advice on exercise and nutrition as with supporting information leaflets were acceptable to older people and helped to improve functional performance (Travers et al 2020). (Appendix 1 exercise and nutrition leaflets ).

In mental health consultations, advice on exercise and nutrition is often provided mental well-being benefits but it is not discussed in relation to building resilience and preventing frailty (Traver et al In press).

In this study we aim to test the acceptability and feasibility of replicating the above intervention for older patients attending MH consultations with the candidate ANP [AK].

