## Appendix patient information leaflets

**Suggested exercises to build resilience**

Spend 20 minutes doing these exercises, once a day or at least 4 times a week

Repeat each exercise 10 times per minute, and increase to 15 times per minute after 1 month when comfortable

Take a 30 second break between exercises

Choose weights you are comfortable with

Don't do any exercise that causes pain

Walk for 30-45 minutes 3-4 times a week

Strength exercises and dietary protein can delay and reverse frailty (for more information: **Delaying and Reversing Frailty (BJGP, Travers et al)**)

**1**

**2**

**3**

**4**

**5**

**6**

**7**

**8**

**9**

**10**

Commit to doing the exercises at a regular time and place to help build a positive habit

Permissions for use of images granted by subject. Some exercises adapted from Serra-Prat et al (Age Ageing)

- **PLAN YOUR MEALS** to include good protein sources
- Aim to eat 20g of protein **WITHIN 1 HOUR OF EXERCISING** for best muscle building, with the balance of daily protein at regular intervals throughout the day
- **VARY YOUR DIET** to keep it interesting and to benefit from a variety of proteins
- **ENCOURAGE OTHERS** by eating with your partner, family or friends
- **PLANT-BASED PROTEIN IS BETTER** for our heart and the environment
- **BE MINDFUL OF ALLERGIES** to eggs, dairy, fish, peanuts, shellfish & soy beans

For more information about reversing frailty and building resilience see:  
Travers et al, BJGP

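### Change in the leaflet's strength exercises cannot be estimated because baseline does not ask about them, and one walking duration code straddles the leaflet's 30-minute minimum

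*Combined protocol and SAP*

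**What the plan says.** The Outcomes section (Exercise) lists two items for baseline and follow-up: "vigorous exercise frequency and duration over past 7 days, and Walking for exercise frequency and duration over past 7 days". Both are coded in bands. For frequency: "Frequency was rated on a 4 point scale (not at all=0; 1-2 times=1, 3-4 times=2 or >4 times=3". For duration: "Duration (0=not applicable, 1=10-30 mins, 2=31-60 mins, 3> 60 mins". The two codes are multiplied to give a score for each item.

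The leaflet's own exercises get a separate item, introduced with the words "Post intervention, we added an additional question specific to the exercises on the information leaflet". Its days code runs from 0 to 5 and its duration code from 0 to 4.

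The leaflet in the Appendix asks for 20 minutes of the exercises daily, or on four or more occasions a week, and calls them strength exercises. The section on intervention components describes them as low risk, with chair support and sit-to-stand movements. On walking the leaflet says "Walk for 30-45 minutes 3-4 times a week".

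The Study Design section describes one group measured before and after. Objective (e) is self-reported adherence at 1 and 3 months. The Analysis section plans non-parametric paired comparisons of pre and post data.

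**The concern.** With no control group, a change in behaviour can be shown only against the patient's own baseline. The behaviour that the leaflet mainly teaches is strength work, and neither baseline item names it. The paired comparison can therefore cover vigorous exercise and walking, but not the exercise at the centre of the advice.

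For walking, a before-and-after measure exists, but its duration bands were not drawn around the leaflet's target. The lower limit of the target, 30 minutes, is the top value of the lowest band. Some patients who follow the advice will be recorded exactly like patients who walk for a third of the advised time, and objective (e) cannot be answered for them.

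**Working it through.** **Strength exercises.** The listed items, by time of asking:

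| Behaviour | Baseline | 3 months |
|---|---|---|
| Vigorous exercise | yes | yes |
| Walking for exercise | yes | yes |
| Leaflet exercises | no | yes |

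A paired difference needs both columns. The third row has one, so no difference can be formed.

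**What the leaflet item can show.** Its largest score is 5 × 4 = 20, which reproduces the stated range of 0 to 20. For adherence, the relevant part is the days code, "Frequency (None=0, 1 day=1, 2 days=2; 3 days=3, 4 days=4, 5 days=5". It separates 0–3 days from 4 or more, which matches the leaflet's weekly minimum if sessions are at most one a day and 6 or 7 days are entered under the top code. The product is less clear:

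- Score 8 is 4 days × 11–20 min (4 × 2) or 2 days × over 30 min (2 × 4).
- Score 12 is 4 days × 21–30 min (4 × 3) or 3 days × over 30 min (3 × 4).
- The 11–20 minute band also mixes the advised 20 minutes with 11–19.

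The components therefore carry information that the product loses.

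**Walking.** I read the leaflet's target as a minimum: 30 minutes or more, three or more times a week. Each combination of non-zero codes is then classified, with the product score in brackets:

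| Times a week (code) | 10–30 min (1) | 31–60 min (2) | over 60 min (3) |
|---|---|---|---|
| 1–2 (1) | not met [1] | not met [2] | not met [3] |
| 3–4 (2) | **undetermined** [2] | met [4] | met [6] |
| over 4 (3) | **undetermined** [3] | met [6] | met [9] |

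A frequency or duration code of 0 is not met. Of the nine cells, 3 are not met, 4 are met and 2 are undetermined. In the undetermined cells, duration runs from 10/30 = 33% to 30/30 = 100% of the advised minimum.

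Using only the product adds to the problem. Scores 2 and 3 each combine an undetermined cell with a not-met cell, so four cells become unreadable instead of two.

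**Effect on a reported proportion.** If k of n patients are undetermined, the proportion meeting the walking advice is known only to within a range of width k/n. Each patient adds 1/20 = 5.0 points at n = 20, or 1/15 = 6.7 points at n = 15.

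**Effect on change.** A patient going from 10 to 30 minutes at 3–4 times a week scores 2 × 1 = 2 both times, a change of 0. Going from 30 to 31 minutes moves the score from 2 to 2 × 2 = 4. Movement between codes is visible; movement within the lowest band is not.

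**The case against.** The strongest reply is that this is a feasibility study of 15–20 patients with mainly descriptive analysis. Change in exercise is not a listed objective: objective (f) concerns frailty and overall physical and mental health. The Analysis section itself says that the numbers do not support a full analysis. This limits the weight of the point. It does not remove it, because the 3-month questionnaire repeats the baseline measures, paired comparison is planned, and the study sets out to test its own data collection.

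The full questionnaire is not in the documents, and the Outcomes section mentions adherence questions in the plural. The conclusion therefore rests on the items that are listed.

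A reader might infer more than the documents support:

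- **That adherence to the leaflet exercises cannot be read.** It can only be asked after the leaflet is given, so the timing is no fault for that purpose, and the days code identifies the weekly minimum.
- **That patients already doing such exercises will inflate apparent uptake by some stated amount.** The Background says "In mental health consultations, advice on exercise and nutrition is often provided mental well-being benefits", but it does not mention strength work or say that patients do any. No size can be derived.
- **That the vigorous-exercise item will rise spuriously at 3 months.** This is only a possibility. The nurse completes the questionnaire with the patient, and the leaflet exercises have their own item by then.
- **That everyone walking 30 minutes or less is unclassifiable.** Those walking fewer than three times a week miss the target whatever the duration.
- **That the upper limit of 45 minutes is also lost within the 31–60 band.** It is, but this does not matter when the target is read as a minimum.

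**Conclusion.** The point holds in two limited parts. First, change in the leaflet's strength exercises cannot be estimated, because the only listed item on them has no baseline value and there is no comparison group. Adherence to them after the intervention remains readable from the days code. Second, patients who walk three or more times a week with duration code 1 cannot be classed as meeting or missing the walking advice. Ordinal change in walking remains readable, and the 3–4 times band fits the leaflet.

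The number of patients affected by the second part is unknown. It could be anything from none to all 15–20, at 5.0 to 6.7 percentage points each. That size assumes that the target is a minimum and that the listed items are the whole exercise measure. This is an inexpensive improvement worth making, not a flaw that undermines the feasibility aims.

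**What to change.** - **Strength exercise.** Before the advice is given, ask about strength or chair exercises over the past 7 days, in days and minutes. Repeat the question at 3 months beside the leaflet item. State on the questionnaire that these exercises are not to be counted as vigorous exercise.
- **Walking.** Record times per week and minutes per walk as numbers. The present categories can be derived from them. Report the proportion walking at least 30 minutes on at least 3 occasions a week, at baseline and at 3 months.
- **If baseline collection is already complete.** The Outcomes section is partly in the past tense, which does not settle this. In that case, report the frequency and duration components separately, not only their product, and state both limitations.

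The cost is one extra baseline question, numeric entry in place of bands and a slightly longer interview. The new question must come before the advice. No extra visits or staff are needed.

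### The leaflet-exercise question covers 7 days but its day codes stop at 5, so daily exercise looks the same as 5 days; it also leaves open whether the leaflet's walking counts

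*Combined protocol and SAP*

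**What the plan says.** The Outcomes section introduces the item with "Post intervention, we added an additional question specific to the exercises on the information leaflet". The question reads "In the past week (7 days) have you completed the exercises on the information leaflet". The answer has two parts, a day code ("Frequency (None=0, 1 day=1, 2 days=2; 3 days=3, 4 days=4, 5 days=5") and a duration code ("Duration (none =0; 10 mins=1, 11-20 mins=2, 21-30 mins=3, >30 mins=4"). The two are multiplied, and the plan adds "Higher values indicate greater exercise intensity (min score 0 to 20".

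The exercise leaflet in the appendix is titled "Suggested exercises to build resilience". For the numbered exercises it advises "Spend 20 minutes doing these exercises, once a day or at least 4 times a week". A few lines further down it advises "Walk for 30-45 minutes 3-4 times a week".

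Walking also has its own frequency and duration item, one of the two taken from the Yale scale in the Outcomes section. Objective (e) in the Aim section is self-reported adherence to the advice at 1 and 3 months. The plan sets no adherence cut-off.

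**The concern.** Two features of the item do not match the advice it is meant to track.

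- **Day code.** The recall period is seven days and the leaflet's first-named frequency is daily, yet the highest code is five days. That top code is closed. The neighbouring Yale items, by contrast, end in an open category for more than four times. A patient who exercises on six or seven days has no valid answer.
- **Walking.** The leaflet carries both the numbered exercises and a walking recommendation, and the question does not say whether walking is in or out. A patient who only walks could answer in good faith with walking days and minutes.

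What is at stake is the descriptive adherence result for objective (e). With 15-20 patients summarised by medians and interquartile ranges (Sample size and Analysis sections), a few answers coded differently could move that summary. No power or error-rate figure depends on this item.

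**Working it through.** **Inputs.** Day codes 0 to 5, and duration codes 1 (10 min), 2 (11-20 min), 3 (21-30 min) and 4 (over 30 min), from the Outcomes section. Numbered exercises: 20 minutes, daily or at least four times a week. Walking: 30 to 45 minutes, three or four times a week. Both sets of advice come from the exercise leaflet. I assume one session per day and that patients report the minutes the leaflet advises.

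**Formula.** Score = day code x duration code.

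**The plan's own range.** Minimum 0 x 0 = 0 and maximum 5 x 4 = 20. This reproduces the stated 0 to 20 and shows that 5 really is the top day code, not a line lost from the text.

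**Scoring the leaflet's advice with the printed codes**

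| Behaviour in the week | Day code | Duration code | Score |
|---|---|---|---|
| Numbered exercises, 20 min, 4 days | 4 | 2 | 8 |
| Numbered exercises, 20 min, 5 days | 5 | 2 | 10 |
| Numbered exercises, 20 min, daily (entered as 5) | 5 | 2 | 10 |
| Walking only, 30 min, 3 days, if counted | 3 | 3 | 9 |
| Walking only, 30 min, 4 days, if counted | 4 | 3 | 12 |
| Walking only, 31-45 min, 3 days, if counted | 3 | 4 | 12 |
| Walking only, 31-45 min, 4 days, if counted | 4 | 4 | 16 |

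If it is counted, walking alone as advised scores 9 to 16. Every such pattern exceeds the 8 for the minimum advised exercise. All but one (three walks of 30 minutes, score 9) exceed the 10 for daily exercise entered as five days.

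**A patient who does both.** Exercising and walking on the same four days and adding the minutes gives 20 + 30 = 50 up to 20 + 45 = 65 minutes. That is code 4, so the score is 4 x 4 = 16, the same as the highest score for walking alone.

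**Effect of extending the day code only.** Daily 20-minute exercise would score 7 x 2 = 14, and the range would become 0 to 7 x 4 = 28. Four walks of 31-45 minutes would still score 16. The longer day field repairs the recording of daily exercise but does not settle the walking question, so the two changes are separate.

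**The case against.** The best defence is that the walking problem may seldom arise. The leaflet ties its 20 minutes to a set of repetitions, rests and weights, and gives walking its own instruction. The Outcomes section calls the item specific to the leaflet exercises. The nurse who delivers the advice also completes the questionnaire with the patient and can steer the answer. Walking has a separate item. The leaflet's layout and the full questionnaire, with any prompts, were not visible in the text I worked from. All of this stands as a reason why the confusion may be uncommon. It does not amount to a written rule, and the documents give none.

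It can also be said that this is a small feasibility study with a descriptive analysis, and that no decision or cut-off rests on this score. That is correct and limits the importance of the point.

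A reader might be tempted to go further in three ways that the documents do not support:

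- *That walking alone can outscore full adherence.* The leaflet advises both activities. If walking counts for everyone, a patient doing both on the same four days scores 16, which walking alone can equal but not exceed. The reversal holds only against the numbered exercises taken alone.
- *That adherence to the exercise frequency cannot be recorded at all.* Codes 4 and 5 both identify patients who reach the leaflet's floor of four. What is lost is the distinction between five, six and seven days.
- *That this is the only adherence measure.* The Outcomes section refers to adherence questions in the plural and to qualitative feedback.

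**Conclusion.** The day-code fault stands without conditions. Six and seven days cannot be coded, so daily exercise is indistinguishable from five days, and a daily 20-minute exerciser scores at most 10 instead of 14.

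The walking fault is a genuine ambiguity with a conditional effect. It matters only if the patient or interviewer counts walking. In that case walking alone as advised scores 9 to 16 against 8 to 10 for the numbered exercises alone. The frequency of this is unknown and cannot be estimated from the documents. The reversal comes mainly from the duration code; the five-day cap only adds to it, since the uncapped 14 is still below 16.

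This is a minor point. It affects how the adherence result can be interpreted and no inferential figure.

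**What to change.** **If the item can still be changed**

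- Let the day field run from 0 to 7 and restate the score range as 0 to 28.
- Word the question as the numbered exercises on the leaflet, not counting walking, and leave walking to its existing item.
- Use the same wording and codes at 1 and 3 months. A change between the two contacts would break their comparability.

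The cost is a reworded question, two more day codes and a corrected range, with no added patient time.

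**If data are already collected.** This is possible, because the Study Design section schedules follow-up to October 2023 and parts of the Outcomes section are in the past tense.

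- Report days and minutes separately as well as, or in place of, the product.
- Label code 5 as five or more days, after checking how any answers of six or seven days were entered.
- State as a limitation that walking may have been counted.

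The check on entry should come before the paper questionnaires are destroyed, which the Data management section plans once data are entered and verified. This route costs a few lines in the report.

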### Aim

The aim of this study is to test the delivery of brief health promotion advice with supporting information leaflets as part of standard clinical consultation for older people attending a community mental health service.

Objectives: The main objectives are to;

- (a) to screen MH patients for frailty using validated tools the clinical frailty scale and SCAR-F
- (b) to test the feasibility of patient recruitment and data collection in the target population
- (c) determine the prevalence of frailty in older adults living with a mental health condition within an outpatient MH service
- (d) examine the acceptability of the brief health promotion advice and information leaflets as part of MH consultation
- (e) examine self-reported adherence to the exercise and nutrition advice at 1 and 3-month follow-up
- (f) Repeat frailty screening and overall physical and mental health at three month follow-up

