### Intervention components

The intervention is delivered by the candidate ANP who is an experienced mental health nurse and is skilled in using motivational interviewing principles to support behaviour change. A normal part of the role is the provision of general health promotion advice for patients in clinics and their home. This aligns with the HSE policy on Making Every Contact Count (<https://www.hse.ie/eng/about/who/healthwellbeing/making-every-contact-count/>).

- Deliver brief Health Promotion advice on exercise and protein nutrition for muscle health to promote resilience and reduce risk of frailty
- Provide patients with information leaflets and clarify expectations for frequency of exercise (Appendix). The exercise and nutrition advise leaflets are used with permission of Travers et al 2022. Both leaflets were deigned based on extensive public patient involvement with older patients, physiotherapist and dietician. The exercises are low risk (use a chair for balance support, sit to stand exercises). Patients with impaired mobility, using Zimmer frame are excluded from study.
- One-month follow-up is undertaken via telephone (or face-to-face if visit scheduled as part of routine care). The one-month follow-up is to encourage adherence to

exercise and nutrition advice and examine adherence and feasibility of undertaking exercise and following diet advice.

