### Analysis

Data analysis uses descriptive statistics. Categorical data is presented as proportions and percentages, continuous data as medians inter quartile ranges. Non-parametric paired statistics is used to compare the pre and post data, however sample size is too small for a comprehensive analysis.

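### The day-by-duration product for the leaflet exercises cannot show who met the leaflet's minimum; for objective (e), report the two codes jointly

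*Combined protocol and SAP*

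**What the plan says.** Objective (e), under Aim, is to "examine self-reported adherence to the exercise and nutrition advice at 1 and 3-month follow-up". Intervention components gives as one purpose of the one-month contact to "examine adherence and feasibility of undertaking exercise and following diet advice".

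In Outcomes, after the general exercise items, the plan states: "Post intervention, we added an additional question specific to the exercises on the information leaflet". Frequency over the past week is coded 0 for none and then one point per day, and is multiplied by a duration code: "4 days=4, 5 days=5); X Duration (none =0; 10 mins=1, 11-20 mins=2, 21-30 mins=3, >30 mins=4". The range is given as 0 to 20, with the interpretation "Higher values indicate greater exercise intensity". No adherence threshold is set for this item, and no separate summary of the two codes is described. The same section says: "The 3-month questionnaire repeated the baseline measures and adherence questions". Those adherence questions are not listed individually.

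The exercise leaflet in the appendix tells patients: "Spend 20 minutes doing these exercises, once a day or at least 4 times a week".

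Analysis has only general rules: "Categorical data is presented as proportions and percentages", and medians with interquartile ranges for continuous data. Data management has the paper questionnaires destroyed after entry and verification.

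**The concern.** The leaflet sets a two-part target, a number of sessions and a length for each. A product lets one part compensate for the other, so fewer but longer sessions can equal or exceed the score of someone who did what was asked. If the product is reported for objective (e) as a median and interquartile range, a reader cannot tell how many patients reached the target. As a constructed extreme, a median of 8 with interquartile range 8-8 fits a group all at 4 days x 11-20 minutes, and equally a group all at 2 days x over 30 minutes. The first group is 100% at 4 or more days and the second 0%. That is possible rather than likely in 15-20 patients.

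Two features of the coding add to this. The 20-minute target is the upper edge of the 11-20 band, so it cannot be told apart from 11 minutes. The frequency code ends at 5 days, so a patient who takes the leaflet's daily option has no matching answer.

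Adherence to an unsupervised intervention is a central feasibility result. The two codes could also be lost if only their product were entered before the paper forms are destroyed.

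**Working it through.** **Inputs.** Day codes 1-5 and duration codes 1-4 (Outcomes); leaflet minimum of 20 minutes at least 4 times a week (appendix). Assumptions: duration is per session, and one day stands for one of the leaflet's times.

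**Step 1: reproduce the plan's range.** Score = day code x duration code. The 20 non-zero combinations are:

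| Days | 10 min (1) | 11-20 min (2) | 21-30 min (3) | over 30 min (4) |
|---|---|---|---|---|
| 1 | 1 | 2 | 3 | 4 |
| 2 | 2 | 4 | 6 | 8 |
| 3 | 3 | 6 | 9 | 12 |
| 4 | 4 | 8 | 12 | 16 |
| 5 | 5 | 10 | 15 | 20 |

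The maximum is 5 x 4 = 20 and the minimum 0, as stated.

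**Step 2: the leaflet minimum.** 4 days at 20 minutes scores 4 x 2 = 8. Below 4 days, 2 x 4 = 8 ties with it, and 3 x 3 = 9 and 3 x 4 = 12 exceed it.

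**Step 3: order, with 11-20 minutes counted as met.** Six combinations meet the minimum (scores 8, 10, 12, 15, 16, 20) and 14 do not, giving 6 x 14 = 84 pairs.
- Reversed: 8 v 9, 8 v 12 and 10 v 12, so 3. All involve the 11-20 band.
- Tied: 8 v 8 and 12 v 12, so 2.
- Correct: 84 - 3 - 2 = 79 (94%).

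**Step 4: order, with only 21 minutes or more counted as met.** Four combinations meet the minimum (12, 15, 16, 20) and 16 do not, giving 4 x 16 = 64 pairs: 0 reversed, 1 tied (12 v 12), 63 correct.

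**Step 5: cut-offs.** Every cut-off from 1 to 20 was tried; none is exact under either rule. Examples:

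| Rule for 20 minutes | Cut-off | Wrongly admitted | Wrongly dropped |
|---|---|---|---|
| 11-20 counts | 8 or more | 3 | 0 |
| 11-20 counts | 10 or more | 1 | 1 |
| 11-20 counts | 13 or more | 0 | 3 |
| 21 or more only | 12 or more | 1 | 0 |
| 21 or more only | 13 or more | 0 | 1 |

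**Step 6: recovery of the day code.** Scores 4, 8 and 12 each arise both below 4 days and at 4 or more days. If only the product is stored, frequency is lost at those scores.

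**Step 7: if duration is a weekly total.** 21-30 minutes over 4 days is 21/4 = 5.25 to 30/4 = 7.5 minutes a day, and the top band holds both 31 minutes and the 4 x 20 = 80 minutes advised. The 20-minute part could not then be assessed.

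**The case against.** The strongest reply is that nothing here is yet an error. The plan calls the product intensity, not adherence; it refers to adherence questions that it does not list; objective (e) sets no threshold; and the Analysis section already allows proportions. A reader might infer that the product is the planned adherence result, or that the two answers will be merged at entry. The documents say neither. This stands, and it is why the point is conditional.

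Second, the score ranks patients well: 79 of 84 pairs correct on one rule, 63 of 64 on the other. Pair counts also weight all combinations equally, and the documents do not say how patients will be distributed. A reader might go further and test the score against frequency alone. There, 8 combinations at 4-5 days against 12 at 1-3 days give 96 pairs, with 13 reversed and 4 tied. That overstates the fault: 10 of the 13 reversals involve the 10-minute code, and those patients miss the leaflet's minimum anyway.

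Third, frequency times duration is a legitimate activity score and matches the other exercise items. It need not be removed. What survives is that it cannot say who reached the target.

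Fourth, a bare proportion at 4 or more days would have its own fault: it counts 4 x 1 and 5 x 1, which are 10-minute sessions, as success. This is correct, and it is why that proportion should not be the headline figure. The leaflet's walking advice has its own item in Outcomes and is outside this point.

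**Conclusion.** The point holds in a limited, conditional form. The product is the only written summary of the only listed item specific to the leaflet exercises. If it is used for objective (e), it cannot show who met the leaflet's minimum at any cut-off. A patient exactly at the minimum can rank too low, but most combinations are ordered correctly. The missing code for 6-7 days is a separate gap in the item, because the leaflet offers a daily option.

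The result rests on duration being per session, which the plan does not state, and on days standing in for times, so that two sessions on one day count once. Severity is minor: the study is descriptive, with 15-20 patients, and both codes are already collected. The documents do not support saying that the adherence analysis is wrong, or that the score fails to reflect adherence in general.

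**What to change.** 1. Keep the product as a descriptive activity score if wanted, but do not use it as the objective (e) result.
2. Keep the day code and the duration code as separate variables, and confirm this before the paper forms are destroyed.
3. State that duration is per session, if that is how it was asked, and that 6-7 days are coded with 5. If the item can still be changed, extend it to 0-7 days.
4. Cross-tabulate the two codes at each follow-up where the item is asked.
5. If duration is per session, report the proportion meeting both parts as a range. The lower figure is 4 or more days and 21 minutes or more; the upper is 4 or more days and 11 minutes or more, since the 11-20 band contains the target. Show the proportion at 4 or more days as the frequency component only; like the range, it relies on 6-7 days being coded with 5.
6. If the duration unit cannot be settled, report the cross-tabulation and the frequency proportion, and say that the 20-minute part cannot be assessed.

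Give counts with each proportion, because precision is low. For assumed counts, 10/20 = 50% has an exact 95% interval of 27% to 73%, and 9/15 = 60% one of 32% to 84%.

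Cost: no new data collection, and one small table per follow-up. The downside is a table and a range in place of a single score.
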